2. Allopurinol (ALLO) is first line therapy for gout prevention with emerging uses in other diseases associated with metabolic syndrome. Discovered in the 1940s by researchers at Burroughs Wellcome, including Nobel laureates Elion and Hitchings, ALLO has been first-line therapy for the treatment of hyperuricemia and gout for many years. ALLO is considered a pro-drug with weak pharmacologic effects; it is converted to an active metabolite, oxypurinol (OXY) via aldehyde oxidase, AOX1. OXY is a potent inhibitor of xanthine oxidase, the primary enzyme involved in the synthesis of UA. Though its major use is in the treatment of gout, ALLO is used for other diseases such as tumor lysis syndrome and kidney stones⁵⁻⁷, and is being repurposed for the treatment of diseases associated with metabolic syndrome, e.g., heart failure, stroke and cardiac shock⁸⁻¹¹. Other xanthine oxidase inhibitors are also on the market or in clinical drug development.

3. Recent data from our laboratory challenge the widely accepted mechanism of action of ALLO and OXY as its sole mechanism and suggest a major role for BCRP.

In the first GWAS of ALLO response, we observed a single locus, in ABCG2, strongly associated with response to ALLO in 1300 patients of European ancestry. Previous genomewide association studies have shown ABCG2 and other UA transporters (e.g. GLUT9, URAT1) to be associated with high UA levels¹²⁻¹⁵. However, in our population of gout patients on ALLO, only ABCG2 (and not the other UA transporters) was significantly associated with drug response, i.e., ALLO-induced changes in UA levels. These results suggest that the gene may act on OXY directly. In fact, in exciting follow-up studies in our laboratory, we found that both ALLO and OXY are excellent substrates of ABCG2 in HEK293 cells over-expressing the transporter suggesting that ABCG2 may

function directly in the pharmacokinetics of ALLO/OXY. These results are consistent with other pharmacogenomic studies that show that genetic variants in membrane transporters that affect pharmacokinetics are associated with altered drug response (e.g., SLC01B1 and methotrexate and statin toxicities, and ABCG2 and rosuvastatin response)¹⁶⁻¹⁹. Because of its location on the apical membranes of intestinal and renal epithelia, the data suggest that ABCG2 functions in reducing the intestinal absorption and enhancing the renal secretion of the drugs as it does for several other drugs²⁰⁻²².

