Phase I procedures: Subjects will be asked to come to the clinic after 8 hours of fasting to provide a 10 ml blood sample to determine baseline serum uric acid and creatinine concentrations. Female subjects will be asked to provide a urine sample (20 mL) to ensure no change in pregnancy status. Subjects will be asked to empty their bladder and will then be given a placebo (microcrystalline cellulose). Blood samples will be collected at the following time points via an IV catheter: 0.5, 1, 1.5, 2, 3, 4, 5, 6, 8, 10, 24 hours. Subjects will be asked to collect all urine samples during their stay. The volume of the urine will be recorded and 20 ml of the sample stored at -20°C for analysis of uric acid and creatinine content. The remaining urine will then be stored with all other urine samples from the subject until the last time point. Subjects will be asked to return in the morning for their 24 hour blood draw and final urine sample. Subjects will be asked to turn in any urine from overnight. 20 ml of the 24-hour collective urine sample will be stored at -20°C for analysis of uric acid and creatinine.

Phase II Procedures: Day 1: Subjects will be asked to come to the clinic after 8 hours of fasting to provide a 10 ml blood sample to determine baseline serum uric acid and creatinine concentrations. Female subjects will be asked to provide a urine sample (20 mL) to ensure no change in pregnancy status. Subjects will be asked to empty their bladders and will then be given 300 mg of allopurinol. Blood samples collected at the following time points via an IV catheter: 0.5, 1, 1.5, 2, 3, 4, 5, 6, 8, 10, 24 hours. Subjects will be asked to collect all urine samples during their stay. The volume of the urine will be recorded and 20 ml of the sample stored at -20°C for analysis of uric acid, drug, and creatinine content. The remaining urine will then be stored with all other urine samples from the subject until the last time point. Subjects will be asked to return in the morning for their 24 hour blood draw and final urine sample. Subjects will be asked to turn in any urine from overnight. 20 ml of the 24-hour collective urine sample will be stored at -20°C for analysis of uric acid, drug, and creatinine.

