Days 2-5: The subjects will receive 4 more doses of allopurinol to be taken once a day until their next visit. Their final inpatient visit must be on Day 6. Adherence will be measured via phone calls and patient diaries. Patients will be asked to keep a log of their

food and drinks.

Day 6: Subjects will be asked to return to the clinic after 8 hours of fasting for their final dose of allopurinol. Subjects will be asked to provide a 10 ml blood sample to determine steady-state levels of drug, creatinine, and uric acid. Subjects will be asked to empty their bladder and they will then be given 300 mg allopurinol. Following their final dose, blood and urine samples will be collected following Phase II: Day 1 procedures. Following the 24-hour time point, subjects will return at least two more times for blood and urine collection up to 72 hours post-allopurinol. **In total, subjects will provide approximately 400 ml of blood.** This is less than a typical blood donation of 500 ml and is below minimal risk of 550 ml for healthy subjects.

| Visit | Timing | Collection |
|--|--|---|
| Screening Part 1 | Anytime | Cheek Swab: ABCG2 genotype Questionnaire |
| Screening Part 2 | Within two weeks of Placebo visit | Blood: CBC, HFP, RFP, UA If female - Pregnancy Cheek Swab: HLA*B 5801 |
| Phase 1: Placebo | Before – Fast 8 hours clinic visit | Blood: Baseline- Creatinine, UA During at 0.5, 1,1.5, 2, 3, 4, 5, 6, 8, 10 hours (Creatinine, UA, ALLO/OXY) Urine: Before – females 20 ml for pregnancy test. During- all urine during stay collected |
| Phase 1: Placebo | 24 hours after placebo dose clinic visit | Blood: Creatinine, UA, ALLO/OXY Urine: Turn in what was collected overnight |
| Phase 2: Allopurinol – Oral 300 mg dose | Before – Fast 8 hours Day 1—clinic visit *Must be started within 2 weeks of Day 0 (Placebo Phase) | Blood: Baseline- Creatinine, UA During at 0.5, 1,1.5, 2, 3, 4, 5, 6, 8, 10 hours (Creatinine, UA, ALLO/OXY_) Urine: Before – females 20 ml for pregnancy test. During- all urine during stay collected |
| Phase 2: Allopurinol – Oral 300 mg tablet | 24 hours after first dose Day 2—clinic visit | Blood: Creatinine, UA, ALLO/OXY Urine: Turn in what was collected overnight – pregnancy test Patient given diaries and tablets to take home for Days 3-6 |
| Phase 2: Allopurinol – Oral 300 mg tablet | 48 hours after first dose Day 3 – at home | Patient Diary and phone follow-ups |

| | | |
|---|---|---|

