| Phase 2: Allopurinol – Oral 300 mg tablet | 72 hours after first dose Day 4 – at home | Patient Diary and phone follow-ups |
| Phase 2: Allopurinol – Oral 300 mg tablet | 96 hours after first dose Day 5 – at home | Patient Diary and phone follow-ups |
| Phase 2: Allopurinol Final Oral 300 mg tablet | 120 hours after first dose Before – Fast 8 hours Day 6 – clinic visit | Blood: Baseline- Creatinine, UA, ALLO/OXY During at 0.5, 1,1.5, 2, 3, 4, 5, 6, 8, 10 hours (Creatinine, UA, ALLO/OXY) Urine: Before – females 20 ml for pregnancy test. During- all urine during stay collected |
| Phase 2: Allopurinol – Follow-up | 24 hours after final dose Day 7 – clinic visit | Blood: Creatinine, UA, ALLO/OXY Urine: Turn in urine that was collected overnight |
| Phase 2: Allopurinol – Follow-up | Day 8 – clinic visit | Blood: Creatinine, UA, ALLO/OXY |
| Phase 2: Allopurinol – Follow-up | As close as possible to 72 hours after injection Day 9 – clinic visit | Blood:, Creatinine, UA, ALLO/OXY |

ANALYTICAL METHODS: Measurement of allopurinol and oxypurinol will be performed by high performance liquid chromatography and mass spectrometry (LC-MS/MS). Measurement of uric acid and its precursors, xanthine and hypoxanthine, will be measured via Amplex Red and Abcam colorimetric assays.

Genotyping: All recruited subjects will sign informed consents and HIPAA forms. At screening, a blood sample (10 mL) or saliva sample will be obtained for DNA extraction. Plasma will be stored for assays of endogenous compounds and drugs. The ABCG2 variants will be genotyped at UCSF by a Taq Man Assay using primers and probes from ABI. The reaction will be run on an ABI 7900 HT.

HLA genotyping and wellness panels will be analyzed by qualified personnel at OMI or other reputable company as approved by [name] or other study personnel.

STATISTICAL ANALYSIS:

Mechanistic pharmacokinetic modeling will be conducted to characterize the pharmacokinetics of allopurinol (ALLO) and oxypurinol (OXY). The mechanistic model will characterize details relevant for this study such as conversion mechanism from ALLO to OXY and estimation of fraction of metabolized drug; estimation of ALLO and OXY renal and secretory clearance; possible concentration-dependent saturation

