mechanism of secretory clearance and consequent longitudinal changes in OXY secretory CL and influence of pharmacogenomics (ABCG2) and demographic covariates (creatinine clearance, age, gender, race and body weight) on secretory and renal CL. By use of the physiological model, we will also attempt to estimate the drug concentration in the renal tubule; by knowing plasma and urinary concentration of OXY, and by estimating filtration and secretory clearance of OXY, we will be able to estimate the time profile of tubular concentrations of OXY. These tubular OXY concentrations represent concentration at the proposed site of action and they will further be linked with the pharmacodynamic response. A model describing concentration dependent inhibition of UA re-absorption from the renal tubule by OXY will be implemented. We will examine linear and non-linear (Emax type of model) relationships between tubular OXY and inhibition of UA reabsorption. In the pharmacokinetic modeling, we expect to see a significant influence of creatinine clearance on renal clearance and a significant influence of ABCG2 genotype on secretory CL and oral bioavailability, as described below. In the pharmacokinetic-pharmacodynamic analysis we expect that individuals with higher tubular concentrations of OXY will show the better response in terms of plasma UA lowering resulting in higher urine UA concentrations. Consequently, higher tubular concentrations will be mostly expected in individuals with high secretory clearance, e.g. individuals with ABCG2 141Q/Q, however the modeling may also account for other factors contributing to high tubular concentration, such as higher filtration rates and other factors, therefore providing more granularity and better mechanistic understanding in all processes leading to overall UA physiology. Although this specific PKPD analysis will be focused on the mechanism and role of ABCG2 in UA response to ALLO and OXY, the established mechanistic framework can be used to test the role of potential new pharmacogenetic variants. Longitudinal PKPD modeling using nonlinear mixed effects is a method carrying the most power to separate the signal from the noise; therefore modeling analysis will be associated with at least 80% power to detect differences in primary endpoints (net secretory clearance and change in UA) as described above. In addition to confirming the result of the primary analysis, this analysis will establish a mechanistic representation of the physiology underlying UA metabolism, therefore providing strong support and evidence to our mechanistic hypothesis. Pharmacokinetic parameters including renal clearance, and net reabsorptive or secretory clearance of UA, OXY and ALLO will be calculated from serum and plasma drug levels by standard pharmacokinetic methods. To assess net secretory or reabsorptive clearance of the three compounds, we will subtract $f_u \cdot \text{GFR}$ (where f_u is the unbound fraction of ALLO, OXY or UA and GFR is the glomerular filtration rate), as measured or estimated from serum and urine creatinine values, from renal clearance of ALLO, OXY and UA, directly measured from plasma and urine values. Previously we have used these methods to calculate net secretion (or reabsorption) of several drugs. For pharmacodynamics, differences in DSUA between the genotype groups will be evaluated first with an analysis of variance. If DSUA is not normally distributed, we will evaluate the differences between the genotype groups using a non-parametric Kruskal-Wallis test. We expect individuals with ABCG2 141K/K and 141Q/K will have a reduced response to ALLO (smaller DSUA) than individuals with ABCG2 141Q/Q. In addition, individuals with ABCG2 141K/K will have reduced renal clearance of ALLO and OXY in comparison to other genotypes since we propose that ABCG2 functions as a secretory

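### The genotype effect on oral bioavailability and the fraction metabolized are not identifiable from oral-only dosing without assumptions that the plan does not state

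*Combined protocol and SAP*

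**What the plan says.** **Modelling aims.** The Statistical Analysis section lists among the model's targets "conversion mechanism from ALLO to OXY and estimation of fraction of metabolized drug", and later expects "a significant influence of ABCG2 genotype on secretory CL and oral bioavailability, as described below". What follows that sentence covers tubular concentrations, renal and net secretory clearance, and the comparison of uric acid change between genotypes. It does not say how bioavailability will be estimated. The covariate sentence places ABCG2 on secretory and renal clearance; it names neither bioavailability nor non-renal clearance. The rationale for an absorption effect is only in the Background (items 3 and 4), which argues from the transporter's site: "Because of its location on the apical membranes of intestinal and renal epithelia".

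**Dosing.** On Phase II Day 1 subjects "will then be given 300 mg of allopurinol". The visit table labels this "Phase 2: Allopurinol – Oral 300 mg dose" and the Day 6 dose "Phase 2: Allopurinol Final Oral 300 mg tablet". No intravenous dose and no OXY dose is described. The catheter is for sampling: "Blood samples collected at the following time points via an IV catheter: 0.5, 1, 1.5, 2, 3, 4, 5, 6, 8, 10, 24 hours". The Day 9 row sets its time "As close as possible to 72 hours after injection", which matches no procedure described elsewhere.

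**Measurements.** ALLO and OXY are both assayed. Plasma is sampled and all urine is collected over 24 hours on Day 1 and again on Day 6. The Day 6 text then calls for further blood and urine up to 72 hours, but the Day 8 and Day 9 rows of the table list blood only.

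**Primary endpoints.** The Statistical Analysis section names net secretory clearance and the change in uric acid.

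**The concern.** After an oral dose, a higher exposure or urinary recovery in one genotype can mean that more drug was absorbed or that less was lost by non-renal routes. An intravenous reference would separate the two for ALLO, and a dose of OXY would do so for the metabolite; the design has neither. The model can still return numbers for bioavailability and fraction metabolized, but they will rest on whatever is held fixed or left out.

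The covariate sentence makes this concrete. If genotype may act on renal clearance and F but not on non-renal clearance, a genotype difference in non-renal loss will tend to be reported as a difference in absorption. The absorption part of the mechanistic conclusion would then rest on an untested assumption.

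**Working it through.** **1. The plan's own figure.** The plan gives no figure for F or fraction metabolized. Its one power figure (80% for a 40% change in allopurinol clearance, 5 per genotype) comes without SD, alpha or test, so it can be neither reproduced nor refuted. Nothing below depends on it.

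**2. What the data determine.** Take one compartment for ALLO feeding one for OXY, with ten parameters:
- absorption rate ka; F (dose reaching the circulation as ALLO); Fp (dose converted before the circulation and arriving as OXY)
- ALLO volume V; ALLO clearances CLr (renal), CLm (to OXY), CLo (other)
- OXY volume Vm; OXY clearances CLrO (renal), CLnO (non-renal)

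Fraction metabolized is fm = CLm/(CLr + CLm + CLo). The plasma and urine profiles of both analytes depend only on eight quantities: ka, F/V, (CLr + CLm + CLo)/V, CLr, Fp/Vm, CLm/Vm, (CLrO + CLnO)/Vm and CLrO.

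A numerical check used the protocol's plasma times, six daily 300 mg oral doses, and urine observed at every sampling time (more than is planned). The sensitivity matrix had rank 8 for 10 parameters, or 7 for 9 with Fp set to zero. Two combinations are therefore not estimable.

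**3. Size of the ambiguity in F.** Illustrative starting values (assumptions, not from the documents): ka 1.2/h, F 0.70, Fp 0.10, V 60 L, CLr 5, CLm 20 and CLo 17 L/h, Vm 40 L, CLrO 1.2 and CLnO 0.1 L/h. These sets give the same profiles (difference below 1e-14):

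| F | V (L) | Non-renal CL (L/h) | F/V | Total CL/V | fm |
|---|---|---|---|---|---|
| 0.49 | 42 | 24.4 | 0.0117 | 29.4/42 = 0.70 | 20/29.4 = 0.68 |
| 0.70 | 60 | 37.0 | 0.0117 | 42/60 = 0.70 | 20/42 = 0.48 |
| 0.875 | 75 | 47.5 | 0.0117 | 52.5/75 = 0.70 | 20/52.5 = 0.38 |

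**4. Fraction metabolized with F fixed at 0.70.** Change CLm from 20 to 36, CLo from 17 to 1, Vm from 40 to 72, Fp from 0.10 to 0.18 and CLnO from 0.10 to 1.14. Then CLm/Vm stays at 0.50, Fp/Vm at 0.0025 and (CLrO + CLnO)/Vm at 0.0325. The profiles are again identical, but fm moves from 20/42 = 0.48 to 36/42 = 0.86.

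**5. Assumptions that restore identifiability.**
- Closed mass balance (ALLO cleared only renally or to OXY, OXY only renally): 7 of 7 parameters estimable without presystemic conversion, 8 of 8 with it.
- V known: 8 of 9. V and Vm both known: 8 of 8. The documents supply neither value.
- V common to the genotypes: the ratio of F/V is the ratio of F, so relative F is estimable.

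**6. What closure gives when true and when false.** Here F is total Day 6 urinary recovery over dose, and fm is OXY over that total.
- True, no presystemic conversion (F 0.70, CLr 5, CLm 35, so fm = 35/40 = 0.875): estimates 0.69 and 0.873.
- False (values of step 3): steady-state recovery = 0.70 × [5/42 + (20/42)(1.2/1.3)] + 0.10(1.2/1.3) = 0.391 + 0.092 = 0.483. OXY share = (0.308 + 0.092)/0.483 = 0.83. The Day 6 simulation agrees: 0.48 (true F 0.70) and 0.83 (true fm 0.48).
- True, but with 0.30 of the dose converted presystemically (F 0.50): the OXY share is 0.92 (true 0.875), and recovery is 0.79, which reflects F + Fp = 0.80.

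**7. A genotype contrast.** Assume recoveries of 70% (Q/Q) and 80% (K/K), equal renal clearance, and drug treated as one substance, so recovery = F × renal share.
- Absorption explanation: F ratio = 0.80/0.70 = 1.14.
- Non-renal explanation: F = 0.90 in both, renal shares 0.70/0.90 = 0.778 and 0.80/0.90 = 0.889, so the non-renal share falls from 22% to 11%. Total clearance ratio = 0.778/0.889 = 0.875.

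Recovered amount is renal clearance × AUC, so the AUC ratio is 1.14 under both. Half-life differs if V is common: unchanged under the first, 1/0.875 = 1.14 times as long under the second. The two coincide completely only if V also falls to 0.875 of its Q/Q value.

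**8. The common non-renal clearance route.** If renal clearance is equal, relative F is the AUC ratio. If it differs, as the plan expects, the renal share s is needed too. For an assumed 40% fall in renal clearance with F unchanged, the recovery ratio is [0.6s/(0.6s + 1 − s)]/s = 0.79, 0.88 and 0.94 at s = 0.6, 0.8 and 0.9. An observed recovery ratio must be divided by that factor to give relative F.

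**The case against.** The strongest reply is that the design is richer than oral-only dosing suggests. Parent and metabolite are measured in plasma and urine on two occasions, with 11 post-dose plasma samples to 24 hours each time. Non-renal clearance enters the elimination rate constant and F does not, so the time course carries information that AUC and recovery lack. Bioavailability is also a single clause of expectation, with no endpoint or test attached.

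Much of this stands, and it rules out several stronger readings that a reader might infer:
- **That F and fraction metabolized cannot be estimated at all.** Steps 5 and 6 show that they can under common volume (relative F) or closed mass balance. What is missing is the stated assumption and a test of it.
- **That the recovery contrast alone shows the two explanations to be indistinguishable.** It does so for recovery and AUC, or if volume also differs; with common volume, half-life separates them.
- **That even the direction of an F effect is arbitrary, because lower renal clearance also lowers recovery.** The plan measures renal clearance directly, so a model with genotype on renal clearance accounts for that fall.
- **That equal non-renal clearance is doubtful under the plan's own hypothesis.** The Background gives ABCG2 two roles, in absorption and renal secretion, and assigns conversion to aldehyde oxidase. It proposes no ABCG2 effect on non-renal systemic loss.
- **That the primary endpoints are compromised.** Renal clearance is urinary amount over AUC, and net secretion subtracts the filtered part. Neither uses F, and nor does the change in uric acid.

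The reply does not supply the missing assumptions. Each route needs one, and the plan states none.

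**Conclusion.** The point holds as a gap in identification. With oral ALLO only and no OXY dose, the trial's own data leave two parameter combinations undetermined, and both quantities named in the plan are affected. In the illustrative model, F could lie anywhere from 0.49 to 0.875, and fraction metabolized from 0.48 to 0.86 at fixed F, with no change in any observable. A closure assumption that is false moved F from 0.70 to 0.48 and fraction metabolized from 0.48 to 0.83.

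Those sizes rest on assumed parameter values; the rank deficiency is structural within the one-compartment model used. The documents give no variability figures, so whether five subjects per genotype could resolve a 14% difference in half-life is unknown. The consequence is confined to what may be concluded about absorption and conversion. It deserves correction because the plan announces findings that the design does not deliver unaided.

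**What to change.** 1. Report any genotype effect on F only as relative bioavailability, conditional on a stated volume or non-renal clearance common to the genotypes. If the second is chosen and renal clearance differs, state the renal share used and show a range.
2. Fit the rival model with genotype on non-renal clearance. Compare it with the bioavailability model on elimination half-life as well as AUC and urinary recovery, and report both, including when the comparison is inconclusive.
3. Report fraction metabolized only under stated closure assumptions, with a sensitivity range for incomplete recovery and presystemic conversion. Otherwise drop it as a separate estimate.
4. Replace the pointer to a description below with the method and its assumptions.
5. Reconcile the Day 6 text (blood and urine to 72 hours) with the blood-only Day 8 and Day 9 rows, because urinary recovery supports any mass balance. Reconcile also the Day 9 reference to an injection with the oral dosing described elsewhere.

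The cost is analysis-plan wording, one additional model fit and a weaker claim about absorption.
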